8.2 Baseline Laboratory Assessment

- Draw blood samples for daily laboratory monitoring
- Draw blood samples for every-72-hour laboratory monitoring
- Draw blood samples for IL-6 and IL-2R anytime between screening and just prior to SFISD

After drawing blood samples, proceed to randomization. These blood tests may be performed on blood already drawn in the previous 12 hours prior to randomization.

8.3 Randomization

• Randomize patient as per study randomization procedure.

8.4 Start of First Infusion of Study Drug (SFISD) 0 hour

The SFISD should begin within 12 hours of the patient or LAR providing informed consent.

Perform the following procedures immediately prior to the SFISD:

- Record concomitant medications
- If the time between randomization and the SFISD is >6 hours:
 - Record the current vital signs
 - o Record the current SpO₂ and the FiO₂
 - o Record ABG and time drawn if performed as part of standard of care
- Infuse the first dose of study drug
 - Record the time of the SFISD
 - o Record the time when the infusion is finished

8.5 24 hours

24 (\pm 2 hours) hours from the SFISD:

- Record concomitant medications
- Record vital signs
- Record the lowest SpO₂ in the previous 24 hours and the time it was performed. The FiO₂ at the time of the SpO₂ measurement will also be recorded
- Record the SpO₂ and the FiO₂ at the time of the assessment
- Record ABG and time drawn if performed as part of standard of care
- Complete Daily Assessment Ordinal Scale
- Perform AE/SAE assessment
- Draw blood samples for daily laboratory monitoring prior to the second infusion of study drug (-2 hour). Daily laboratory monitoring may be performed on blood drawn in the previous 12 hours
- Draw blood for PK analysis together with daily laboratory monitoring. The PK specimens may be obtained from blood drawn in the previous 12 hours. The time of the draw must be recorded
- Start the infusion of second dose of study drug 24 hours (±1 hour) from the SFISD
 - o Record the time when the infusion starts and finishes

8.6 48 hours

48 hours (± 2 hours) from the SFISD:

- Record concomitant medications
- Record vital signs
- Record the lowest SpO₂ in the previous 24 hours and the time it was performed. The FiO₂ at the time of the SpO₂ measurement will also be recorded
- Record the SpO₂ and the FiO₂ at the time of the assessment
- Record ABG and time drawn if performed as part of standard of care
- Complete Daily Assessment Ordinal Scale
- Perform AE/SAE assessment
- Draw blood samples for daily laboratory monitoring prior to the third infusion of study drug (-2 hour). Daily laboratory monitoring may be performed on blood drawn in the previous 12 hours
- Draw blood for PK analysis together with daily laboratory monitoring. The PK specimens may be obtained from blood drawn in the previous 12 hours. The time of the draw must be recorded
- Start the infusion of third dose of study drug 48 hours (±1 hour) from the SFISD
 - o Record the time that the infusion starts and finishes

8.7 72 hours

For patients who remain hospitalized 72 (± 2 hours) from the SFISD:

- Record concomitant medications
- Record vital signs
- Record the lowest SpO₂ in the previous 24 hours and the time it was performed. The FiO₂ at the time of the SpO₂ measurement will also be recorded
- Record the SpO₂ and the FiO₂ at the time of the assessment
- Record ABG and time drawn if performed as part of standard of care
- Complete Daily Assessment Ordinal Scale
- Perform AE/SAE assessment
- Draw blood samples for daily laboratory monitoring. Daily laboratory monitoring may be performed on blood drawn in the previous 12 hours
- Draw blood samples for every-72-hour laboratory monitoring. 72-hour laboratory monitoring may be performed on blood drawn in the previous 12 hours
- Draw blood for PK analysis together with daily laboratory monitoring. The PK specimens may be obtained from blood drawn in the previous 12 hours. The time of the draw must be recorded

8.8 96, 144, 192 and 240 hours

For patients who remain hospitalized 96, 144, and 192 hours (±4 hours) from the SFISD:

- Record concomitant medications
- Record vital signs
- Record the lowest SpO₂ in the previous 24 hours and the time it was performed. The FiO₂ at the time of the SpO₂ measurement will also be recorded
- Record the SpO₂ and the FiO₂ at the time of the assessment
- Record ABG and time drawn if performed as part of standard of care
- Complete Daily Assessment Ordinal Scale
- Perform AE/SAE assessment
- Draw blood sample for IL-6 and IL-2R at 96 hours. IL-6 and IL-2R may be performed on blood drawn in the previous 12 hours
- Draw blood samples for every 72-hour laboratory monitoring at 144 hours. 72-hour laboratory monitoring may be performed on blood drawn in the previous 12 hours
- Draw blood samples for daily laboratory monitoring. Daily laboratory monitoring may be performed on blood drawn in the previous 12 hours

8.9 120, 168, and 216 hours

For patients who remain hospitalized 120, 168, and 216 hours (±4 hours) from the SFISD:

- Record concomitant medications
- Record vital signs
- Record the lowest SpO₂ in the previous 24 hours and the time it was performed. The FiO₂ at the time of the SpO₂ measurement will also be recorded
- Record the SpO₂ and the FiO₂ at the time of the assessment
- Record ABG and time drawn if performed as part of standard of care
- Complete Daily Assessment Ordinal Scale
- Perform AE/SAE assessment
- Draw blood samples for daily laboratory monitoring. Daily laboratory monitoring may be performed on blood drawn in the previous 12 hours
- Draw blood samples for every 72-hour laboratory monitoring at 216 hours. 72-hour laboratory monitoring may be performed on blood drawn in the previous 12 hours

8.10 Days 12 to 28

For patients who remain hospitalized 12, 14, 16, 18, 20, 22, 24, 26, and 28 days (±4 hours) from the SFISD:

- Record concomitant medications
- Record vital signs
- Record the lowest SpO₂ in the previous 24 hours and the time it was performed. The FiO₂ at the time of the SpO₂ measurement will also be recorded
- Record the SpO₂ and the FiO₂ at the time of the assessment
- Record ABG and time drawn if performed as part of standard of care
- Complete Daily Assessment Ordinal Scale
- Perform AE/SAE assessment

Patients discharged prior to Day 12 with the need for supplemental oxygen will be contacted on Day 12 to determine if they are still receiving supplemental oxygen.

8.11 Day 60 and Day 30

Patients who have been discharged from the hospital before Day 25, will be followed-up on Day $30 \ (\pm 5 \ days)$ for an AE/SAE assessment as well as to determine if they are receiving supplemental oxygen. For patients discharged from the hospital on Days 25-29, the final inpatient safety assessment will substitute for the Day 30 safety and mortality assessment. The Day 30 safety and mortality assessment may be conducted with an HCP.

Patients, who have been discharged from the hospital before Day 55, will be contacted on Day $60 \ (\pm 5 \ days)$ to determine if they are receiving supplemental oxygen, experienced any symptoms suggestive of long COVID, and developed any SAEs since the Day 30 assessment. The Day 60 assessment will be completed as a final inpatient safety assessment for patients who remain hospitalized or are discharged from the hospital on Days 55-59.

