1.3 Pre-Clinical Development of CM4620

1.3.1 Pre-Clinical Safety and Toxicology Studies

Safety pharmacology studies conducted in rats indicated no CM4620-induced adverse effects on central nervous or respiratory systems. Dose-limiting adverse clinical and cardiovascular effects were noted in a single telemetered cynomolgus monkey dosed at 25 mg/kg IV with Auxora. Cardiovascular data at lower doses (1, 3 and 10 mg/kg) showed transient, non-dose-related, slight-to-moderate increases in systolic/diastolic arterial blood pressures and negative chronotropic effects (mild and non-adverse) at all doses and in placebo treated animals.

Repeat-dose toxicity studies conducted in both rats and monkeys showed no observable adverse effect levels (NOAELs) of 25 mg/kg/day and 3 mg/kg/day, respectively. In vitro genetic toxicity studies were negative in the Ames bacterial reverse mutation assay and weakly positive/equivocal in a micronucleus assay conducted in human peripheral blood lymphocytes. A subsequent in vivo micronucleus study conducted in rats involving two different endpoints (bone marrow micronucleus and liver Comet assays) showed no evidence of DNA reactivity. Based on the results of the complete battery of genotoxicity testing, the weight of evidence indicates that CM4620 is neither mutagenic nor clastogenic. Hemolysis testing concluded that CM4620 placebo was compatible with human plasma and non-hemolytic in human blood. Specific local tolerance studies to examine irritation/inflammation at the injection site were not performed, but no evidence of compound-related or vehicle-related local irritation was observed in the repeat-dose toxicity studies in rat and monkey. Finally, in vitro 3T3 results indicated that CM4620 is potentially phototoxic, so appropriate precautions are being taken in clinical trials.

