9.4 Recording Adverse Events

Recording of AEs must begin after randomization. All conditions present before randomization, including untoward medical events during Screening, should be documented as medical history. Documentation shall continue until the patient dies, the patient withdraws consent, or the patient's participation in the study ends. Information to be collected includes:

- Type of event
- Date of onset
- Date of resolution
- Investigator-specified relationship to study drug and assessment of severity
- Seriousness
- Any action taken

While an AE is ongoing, changes in the severity (e.g., worsening and improving) should be noted in the source documents, but when documenting the AE, only the total duration and the greatest severity should be recorded in the case report form. AEs characterized as intermittent require documentation of onset and duration.

All AEs reported or observed during the study must be followed to resolution. Or, if not fully resolved, until the condition has stabilized, the patient dies, withdraws consent, or CalciMedica ends the trial (whichever is first).

Adverse events resulting from concurrent illnesses, reactions to concurrent medications, or progression of disease states must also be reported. Pre-existing conditions (present before the start of the AE collection period) are considered concurrent medical conditions and should NOT be recorded as AEs. However, if the patient experiences a worsening or complication of such a concurrent condition, the worsening or complication should be recorded as an AE. Investigators should ensure that the AE term recorded captures the change in condition (e.g., "worsening of...").

Each AE should be recorded to represent a single diagnosis. Accompanying signs (including abnormal laboratory test values or ECG findings) or symptoms should NOT be recorded as additional AEs. If a diagnosis is unknown, sign(s) or symptom(s) should be recorded as an AE(s).

Elective procedures (surgeries or therapies) performed to manage/treat conditions that existed prior to the patient enrolling in the trial should not be recorded as AEs but should be documented in the patient's source documents. If a planned procedure is performed early (e.g., as an emergency) because the pre-existing condition worsens, the worsening condition should be captured as an AE.

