8.1.4.4 Adverse Events

Treatment-emergent AEs (TEAEs) are defined as AEs that started or worsened in severity on or after the SFISD.

All adverse events will be coded from the reported term using the Medical Dictionary for Regulatory Activities (MedDRA) version 23.0 or the later version.

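### Protocol 8.11 conflicts with 9.3, 9.4 and Appendix 2 on non-serious AEs after Day 30, so late TEAE capture can depend on discharge or on site

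*Protocol*

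**What the plan says.** Protocol 8.11 sets what is collected late in follow-up, and the content differs by visit and by discharge date:

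- **Day 30, discharged before Day 25:** follow-up "for an AE/SAE assessment as well as to determine if they are receiving supplemental oxygen".
- **Day 30, discharged on Days 25-29:** no contact, because "the final inpatient safety assessment will substitute for the Day 30 safety and mortality assessment".
- **Day 60, discharged before Day 55:** oxygen use, and whether they "experienced any symptoms suggestive of long COVID, and developed any SAEs since the Day 30 assessment".
- **Day 60, in hospital:** "The Day 60 assessment will be completed as a final inpatient safety assessment for patients who remain hospitalized". The same applies to discharges on Days 55-59.

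Other parts of the plan are broader:

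- **Protocol 9.4**, on AE recording: "Documentation shall continue until the patient dies, the patient withdraws consent, or the patient's participation in the study ends".
- **Protocol 9.3** requires an open, non-directed question at every AE/SAE assessment, plus chart review while the patient is in hospital.
- **Appendix 2** marks the AE/SAE row in the shared column for Days 30 and 60 and has every patient complete both. Footnote e makes the Day 60 visit a phone call for patients discharged before Day 55.
- **SAP 8.1.4.4**: "Treatment-emergent AEs (TEAEs) are defined as AEs that started or worsened in severity on or after the SFISD". Neither this definition nor the tables in SAP 8.7.2 set an end date.

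**The concern.** Section 8.11 names a full AE/SAE assessment for Day 30 and only SAEs for Day 60. A site reading that section alone would reasonably conclude that non-serious AEs are no longer sought by phone after Day 30. A site reading 9.3, 9.4 and Appendix 2 would ask the open question on the same call. Both cannot be right.

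Under the literal reading of 8.11, the collection window for non-serious events is set by discharge, which happens after randomization and which the drug is meant to hasten. The SAP would then put events from unequal windows into one TEAE table. TEAE incidence is a listed safety endpoint that serves a secondary objective. SAP 8.4.3 already recognises that data collection between Day 30 and Day 60 is limited for the primary endpoint and adds a sensitivity analysis for it. The safety tables have no counterpart.

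**Working it through.** **1. The instructions side by side**

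| Patient | Day 30 under 8.11 | Day 60 under 8.11 | 9.3, 9.4 and Appendix 2 |
|---|---|---|---|
| Discharged before Day 25 | AE/SAE assessment | Oxygen, long COVID, SAEs | Open AE question at both |
| Discharged Days 25-29 | Last inpatient assessment stands in | Oxygen, long COVID, SAEs | Open AE question at both |
| Discharged Days 30-54 | Still in hospital | Oxygen, long COVID, SAEs | Open AE question at both |
| Discharged Days 55-59, or in hospital at Day 60 | Still in hospital | Final inpatient safety assessment | Open AE question at both |

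In the second row, 8.11 provides no general AE question after discharge, so the gap can start at Day 25. In the first row it can also start then, because the Day 30 contact has a window of 5 days either side.

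**2. Possible size (illustration only)**

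The plan gives no figure for this point, so I used its planning inputs: 330 recoveries in 400 patients and a recovery rate ratio of 1.43 (Protocol 10.2, SAP 4). Check of the event count: 4 × (1.960 + 1.282)² / (ln 1.43)² = 42.03 / 0.1279, about 329, against 330 stated.

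Let S_P and S_A be the shares not recovered. With a constant ratio, S_A = S_P^1.43, and (S_P + S_A)/2 = 1 − 330/400 = 0.175. This gives S_P = 0.229 and S_A = 0.121, a difference of 0.107. With 266 events in 320 patients (Protocol Table 6) and a ratio of 1.49, the shares are 0.227 and 0.110, a difference of 0.117.

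Protocol 10.2 and SAP 4 tie 400 patients to 30 days; the synopsis says 60. I took the shares as those not recovered at Day 30. On the 60-day reading, the same shares describe patients not recovered at Day 60.

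Assumptions:
- Not recovered means dead or in hospital.
- The true late non-serious AE risk p is the same in both arms.
- Events are captured only in hospital.
- The death proportion d is the same in both arms.

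The artificial difference is p × [(S_P − d) − (S_A − d)] = p × (S_P − S_A), so d cancels:

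| p | 330/400, ratio 1.43 | 266/320, ratio 1.49 |
|---|---|---|
| 5% | 0.54 points | 0.59 points |
| 10% | 1.07 | 1.17 |
| 20% | 2.15 | 2.35 |
| 30% | 3.22 | 3.52 |

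For overall TEAE incidence these are upper figures for a given p. SAP 8.7.2 counts each patient once, so someone with an earlier TEAE adds nothing, and some patients leave hospital after Day 30.

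**3. Direction**

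With deaths d_P and d_A, the sign is that of (S_P − S_A) − (d_P − d_A). It reverses if placebo deaths exceed Auxora deaths by more than 10.7 points on the first set of inputs. For example:
- Deaths of 15% and 3% leave 22.9 − 15 = 7.9% of placebo and 12.1 − 3 = 9.1% of Auxora patients in hospital, so the sign reverses.
- Deaths of 15% and 5% leave 7.9% and 7.1%, so it does not.

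**The case against.** The best reply is that the plan should be read as a whole. Appendix 2 puts an AE/SAE assessment on the Day 60 call, 9.3 attaches the open question to every such assessment, and Protocol 3.1 and SAP 3.1 describe Day 30 and Day 60 in the same terms, as safety and mortality assessments. On that reading the question is already required. The call also asks about long-COVID symptoms, some of which could be recorded as non-serious AEs. Protocol 8.8 to 8.11 list no inpatient visit between Day 30 and Day 60, so the contrast with hospital patients is weaker than it looks. SAP 8.7 makes safety purely descriptive, and limiting late contact to SAEs after a three-dose course is a legitimate choice.

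Most of this stands, and it limits the consequence. It does not settle which instruction sites follow, and if SAE-only contact was the intention, 9.4, Appendix 2 and the TEAE tables do not reflect it.

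Two stronger inferences are not supported. A reader might conclude that late non-serious TEAEs are certain to be recorded only in inpatients. That requires every site to apply 8.11 literally, and even then Day 55-59 discharges have the full assessment. A reader might also link the gap to the statement in Protocol 1.3.1 that "in vitro 3T3 results indicated that CM4620 is potentially phototoxic, so appropriate precautions are being taken in clinical trials", and infer that a delayed light reaction would go unseen. Nothing in the documents says when such a reaction would occur or that it would be non-serious, and patients discharged before Day 25 have a full AE/SAE assessment at Day 30. The Pharmacy Manual and Safety Monitoring Plan, where precautions might be described, are not available here.

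**Conclusion.** The conflict is real and should be resolved. Followed literally, 8.11 makes capture of non-serious TEAEs after about Day 30 (from Day 25 for some) depend on discharge. Followed differently at different sites, it makes capture uneven between sites.

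The likely distortion is small: roughly 0.5 to 3 percentage points as an upper illustration. That range rests on an assumed 5-30% late risk, equal deaths by arm, capture only in hospital, and the planning recovery rates. A much higher late risk would give a larger figure, but the documents offer no basis for one. Systematic bias towards Auxora is also not established: with similar mortality the faster-recovering arm would look better, while a large mortality difference could reverse this. On either reading, SAEs and deaths are still sought to Day 60, and no hypothesis test or alpha depends on the TEAE tables.

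**What to change.** Preferred: reconcile Protocol 8.11 with 9.3, 9.4 and Appendix 2, so that the Day 60 call includes the open AE question for all discharged patients, explicitly including those discharged on Days 25-29. For that group the question should cover the period since discharge. The cost is one question on a call already being made and slightly more AE data entry.

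If the call is to stay SAE-only, say so in 9.4 and Appendix 2, and add a sentence to SAP 8.7.2: non-serious TEAEs are compared between arms up to a common Day 30 cut-off, and serious TEAEs and deaths are reported to Day 60. The cost is that late non-serious events leave the main table; they can still be listed. The Day 25-29 discharges would still have a gap of up to 5 days before that cut-off, which should be stated with the table.

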8.12 Discharge Date

The time and date of initial discharge will be recorded, any re-admission and subsequent discharge date, as well as if the patient was sent home on oxygen when discharged, and if the patient was sent to a nursing home.

8.13 Study Assessments

The Daily Assessment-Ordinal Scale will be filled out daily for all patients.

8.13.1 Concomitant Medications

The name, dose and frequency of medications that were administered will be recorded. Generic names should be used when possible. The administration of convalescent plasma, plus the number of units administered, should be recorded as a concomitant medication.

8.13.2 Vital Signs

The patient's temperature, heart rate (beats per minute), systolic and diastolic blood pressures and respiratory rate (breaths per minute) closest to the time of assessment should be recorded.

8.13.3 Arterial Blood Gas

If an arterial blood gas (ABG) has been performed as supportive care, the time of the draw and following results will be recorded: the pH, PaO₂, PaCO₂, SaO₂ and FiO₂.

8.13.4 SpO_2/FiO_2

The SpO₂ will be determined using a hospital approved pulse oximeter. The PI or appropriately trained study coordinator should review the pulse oximetry waveform determining the SpO₂ to attest to its adequacy. The FiO₂ at the time of the SpO₂ measurement will be recorded. For patients with assisted breathing, the FiO₂ is read from the controlled oxygen source e.g. Venturi masks, ventilator and CPAP/BIPAP systems with calibrated oxygen blenders. For patients breathing unassisted i.e. room air, the FiO₂ is recorded as 0.21. If a patient is on an uncontrolled oxygen source, the following table provides the estimated FiO₂:

Table 5. Conversion of O₂ Flow to FiO₂

Supplemental Oxygen L/min	Estimated FiO ₂ (%)								
	Nasal Cannula	Face Mask	Face Mask with Reservoir						
Room Air	21								
1	24								
2	28								
3	32								
4	36								
5	40	40							
6	44	50	60						
7		50	70						
8		60	80						
9		60	90						
10		60	95						

Adapted from Vincent et al., 2009

8.13.5 Laboratory Analyses

CBC with Differential and Serum Chemistries will be performed daily through Day 10.

Ferritin, C-reactive protein, Procalcitonin and D-Dimer will be drawn at the baseline assessment and then every 72 hours until 216 hours.

Blood samples for biomarkers, such as IL-6 and IL-2R, will be drawn twice, once between screening and SFISD and again at 96 hours. If a site is unable to collect blood samples for biomarkers at any time point these tests will not be performed.

CBC results that should be reported in the eCRFs include absolute or percent neutrophil and lymphocyte counts. Serum chemistries reported in CRFs should include sodium, potassium, chloride, bicarbonate, blood urea nitrogen, creatinine, glucose, calcium, phosphorus, as well as magnesium, total protein, albumin, prealbumin, alkaline phosphatase, alanine transaminase (ALT), aspartate transaminase (AST), total bilirubin, lactate dehydrogenase (LDH), total cholesterol, triglycerides, and creatine kinase (CPK). If a site is unable to perform any of these laboratory tests or it is not part of the standard of care testing for the patient, it will not be performed.

A reference laboratory will analyze the blood samples for serum biomarkers, such as IL-6 and IL-2R.

